8.1.1 Temporary Interruption of Study Treatment

The following criteria for temporary interruption of study treatment apply at any time during the 52-week treatment period:

- For those subjects who present with signs and/or symptoms of COVID-19 during the study, the study treatment should be temporarily interrupted while the subject undergoes diagnostic testing for SARS-CoV-2 (see [Section 9.8](#) [SARS-CoV-2 Testing]).
- Study treatment must be temporarily interrupted for subjects who test positive for SARS-CoV-2 until complete recovery (if symptomatic) and a negative molecular test result is obtained. Study treatment may be restarted at investigator discretion following consultation with the BMS Medical Monitor/designee provided that the subject meets the criteria outlined in [Section 9.8](#) (SARS-CoV-2 Testing).
- Study treatment should be temporarily withheld if a subject develops a skin-related AE that is either severe in intensity, or meets the criteria for an SAE (see [APPENDIX 3](#) for definitions), or is sufficient to require temporary discontinuation in the judgment of the investigator. Study treatment should be temporarily withheld until the intensity of the AE decreases or the AE resolves, and may be restarted only after discussion of the case with the BMS Medical Monitor/designee.

Additional criteria for temporary interruption applicable to the **OLE period only** are as follows:

- Study treatment may be interrupted by the investigator for medical procedures not related to UC or for AEs that do not meet criteria for study discontinuation and are assessed by the investigator as not related to the study drug under the following conditions:
 - Documented prior approval from the BMS Medical Monitor/designee
 - Agreement between the investigator and the BMS Medical Monitor/designee that the subject has benefited from study treatment and that temporary interruption (rather than discontinuation) of study drug will result in the greatest benefit to the subject
 - Dose interruption is expected to be 4 weeks or less

Study treatment may be restarted at investigator discretion following consultation with the BMS Medical Monitor/designee provided that there has been adequate resolution of AE or post-procedure condition.

8.1.2 Poststudy Treatment Study Follow-Up

Subjects who discontinue study treatment will continue to be followed for 28 days post last dose of study drug, or longer, as required, and in line with [Section 9.2.3](#) (Follow-up of AEs and SAEs). The posttreatment follow-up visit (Week 56) is not required for subjects who transition to a BMS-sponsored roll-over/follow-on study (eg, Study IM011077).

8.2 Discontinuation from the Study

Subjects who request to discontinue study treatment ([Section 8.1](#)) will remain in the study and continue to be followed for protocol-specified posttreatment follow-up procedures. The only exception to this is when a subject specifically withdraws consent for any further contact with him/her or persons previously authorized by subject to provide this information.

- Subjects should notify the investigator of the decision to withdraw consent from future follow-up **in writing**, whenever possible.
- The withdrawal of consent should be explained in detail in the medical records by the investigator and entered on the appropriate eCRF page.
- In the event that vital status (whether the subject is alive or dead) is being measured, publicly available information should be used to determine vital status only as appropriately directed in accordance with local law.
- If the subject withdraws consent for disclosure of future information, the Sponsor may retain and continue to use any data collected before such a withdrawal of consent.

8.3 Lost to Follow-Up

- All reasonable efforts must be made to locate subjects to determine and report their ongoing status. This includes follow-up with persons authorized by the subject.
- Lost to follow-up is defined by the inability to reach the subject after a minimum of **3** documented phone calls, faxes, or emails as well as lack of response by subject to 1 registered mail letter. All attempts should be documented in the subject's medical records.
- If it is determined that the subject has died, the site will use permissible local methods to obtain date and cause of death.
- If investigator's use of third-party representative to assist in the follow-up portion of the study has been included in the subject's ICF, then the investigator may use a Sponsor retained third-party representative to assist site staff with obtaining subject's contact information or other public vital status data necessary to complete the follow-up portion of the study.
- The site staff and representative will consult publicly available sources, such as public health registries and databases, to obtain updated contact information.
- If after all attempts, the subject remains lost to follow-up, then the last known alive date as determined by the investigator should be reported and documented in the subject's medical records.

8.4 Replacement of Subjects

Subject replacement is not permitted.

8.5 Study Discontinuation

A DMC will provide oversight of the safety of trial subjects as outlined in [Section 5.1.6](#) of the protocol and in the DMC Charter.

The DMC will periodically review safety data and make recommendations regarding the appropriateness of continuing the study, with or without study modifications, or stopping the study.

BMS reserves the right to terminate access to BMS supplied study treatment if any of the following occur: a) the study is terminated due to safety concerns; b) the development of BMS-986165 is terminated for other reasons, including but not limited to lack of efficacy and/or not meeting the study objectives; c) the participant can obtain medication from a government sponsored or private health program. In all cases BMS will follow local regulations.

9 STUDY ASSESSMENTS AND PROCEDURES

Study procedures and timing are summarized in the Schedule of Activities ([Section 2](#)). Waivers or exemptions from protocol-required evaluations are not allowed.

All immediate safety concerns must be discussed with the BMS Medical Monitor/designee immediately upon occurrence or awareness to determine if the subject should continue or discontinue treatment.

Adherence to the study design requirements, including those specified in the Schedule of Activities (Section 2), is essential and required for study conduct.

All screening evaluations must be completed and reviewed to confirm that potential subjects meet all eligibility criteria before randomization. The investigator will maintain a screening log to record details of all subjects screened and to confirm eligibility or record reasons for screening failure, as applicable.

Procedures conducted as part of the subject's routine clinical management (eg, complete blood count) and obtained before signing of the ICF may be utilized for screening purposes provided the procedure meets the protocol-defined criteria and this approach has been discussed and agreed with the BMS Medical Monitor/designee (Section 2). A CXR performed less than 6 months prior to signing of the ICF may be used in place of the screening CXR, provided the subject has no symptoms or signs suggestive of pulmonary disease in the interim.

Assessments at the randomization visit (Day 1) must be performed per protocol. Standard of care assessments may not be used to establish pretreatment baseline parameters (ie, at the randomization visit). Procedures not specified in the protocol that are part of standard care may be performed if they do not interfere with study procedures. Any data arising from such procedures are not to be reported in the eCRF.

The study data includes all the information that is collected as a result of the study, including participant demographics, disease characteristics, clinical information, blood tests, biomarker tests, endoscopic videos, intestinal biopsies obtained during endoscopy, and other tests listed in

Table 1. Study data collected during this study will be used to help us understand how BMS-986165 works in people with UC, and related health conditions. The study data may also be used to help us understand the biology of UC and related health conditions, how study tests perform in people with UC, and for other relevant health research relating to BMS-986165 or these health conditions.

9.1 Efficacy Assessments

Every effort must be made to ensure that the same evaluator(s) complete the assessment for each subject. If the evaluator(s) is unable to complete the evaluation, then a qualified individual with overlapping experience may perform the evaluation. Documentation of who performed the evaluation is to be recorded in source documents. Assessments are to be performed at approximately the same time of day throughout the duration of the study.

9.1.1 Capturing Data to Assess Disease Activity and Determine Efficacy

- **Subject's Electronic Daily Diary:** An electronic diary will be provided to each subject for daily recording of SF and RB data. **Baseline SF** (either reference remission SF or pre-UC SF; see Mayo score, below) and **health-related quality of life** (Inflammatory Bowel Disease Questionnaire [IBDQ]) will also be captured in the electronic diary at the timepoints indicated in the Schedule of Activities ([Section 2](#)).

Data derived from the electronic daily diary are used for assessment of Inclusion Criteria and outcome measures. Subjects will be trained on the use of the electronic diary at the screening visit. Sites should periodically assess subject compliance with the electronic daily diary. Should the subject miss daily entries prior to a study visit, the investigator should assess if the visit should be rescheduled to ensure that an adequate number of daily entries for efficacy assessment are recorded.

- **Medidata Rave Electronic Data Capture (EDC):** The **PGA** (see Mayo score, below) and **UC-related medical resource utilization** (see [Section 9.7](#)) will be evaluated by the investigator or designee and recorded in the Medidata Rave EDC system at the timepoints indicated in the Schedule of Activities ([Section 2](#)).
- **Endoscopy:** Endoscopy (colonoscopy or flexible sigmoidoscopy) will be performed at the timepoints indicated in the Schedule of Activities

• **Endoscopic biopsies:**

• **Serum high-sensitivity C-reactive protein (hsCRP):**

• **fecal lactoferrin:**

9.1.2 Disease Activity and Quality of Life Indices Used in this Study

The following instruments will be used to assess UC disease activity and health-related quality of life during the study as indicated in the Schedule of Activities (Section 2). Selected endpoints that use these indices are defined in [Table 10](#):

- **Total Mayo score:** The **total Mayo score** is a composite disease activity index that is comprised of 4 subscores: SF, RB, and ES subscores, and a PGA subscore.⁴⁷ Consistent with regulatory draft guidance, the ES subscore scale has been modified so that friability is no longer included in the definition of an ES subscore = 1.^{38,48} Each subscore is scored on a 4-point scale, ranging from 0-3, leading to a maximum total score of 12. Higher scores indicate more severe disease. The total Mayo score may be determined at screening and/or Day 1 and at Weeks 12 and 52, and ET visit (if applicable). It will be used in endpoint assessment.
- **Modified Mayo score:** The **modified Mayo score** is a composite of the following total Mayo score subscores: SF, RB, and ES.³⁸ Friability is not included in the definition of an ES subscore = 1, and the PGA is not included in the calculation of the modified Mayo score.^{38, 39, 48} The maximum total score of the modified Mayo score is 9. The modified Mayo score calculated to determine eligibility will be used as the baseline score for randomization on Day 1. The modified Mayo score will also be determined at Weeks 12 and 52, and ET visit (if applicable). It will be used in endpoint assessment.
- Details regarding the recording of the individual Mayo score components and the calculation of the total Mayo score and modified Mayo score are provided in [APPENDIX 9](#), while timing of assessments are detailed in the Schedule of Activities (Section 2). Briefly, the investigator records the baseline SF at the screening visit, and the PGA at each study visit, while the subject

records daily SF and RB scores in the study diary. The ES subscore will be determined by a central reader who is blinded to subject details, including visit number and treatment assignment. The investigator will also record an ES subscore (local read) which will be used for post hoc analyses.

- **Partial Mayo score**: The **partial Mayo score** is a composite of the following Mayo score subscores: SF, RB, and PGA.⁴⁹ The partial Mayo score may be determined at the timepoints indicated in the Schedule of Activities ([Section 2](#)).
- **Symptomatic Mayo score**: The **symptomatic Mayo score** is a composite and defined as the sum of the Mayo SF and RB subscores. It may be calculated at various timepoints and will be used in endpoint assessment.
- **UCEIS**:^{50, 51} The UCEIS is a composite index that evaluates the endoscopic appearance of the mucosa. Three descriptors are scored as follows: vascular pattern (0 to 2), bleeding (0 to 3), and erosions and ulcers (0 to 3), to give a score ranging from 0-8, where higher scores indicate more severe disease ([APPENDIX 10](#)). [REDACTED]

Additional details on endoscopy image acquisition, image quality control and central reading for the assessment of Mayo ES subscore and UCEIS will be provided in the Endoscopy Image Review Charter.

- [REDACTED]

- **UC-100**⁴⁰: The UC-100 is a composite index that uses the weighted Mayo SF subscore, Mayo ES subscore, [REDACTED] to derive a score that ranges from 1 to 100, where higher scores indicate a greater degree of disease activity.⁴⁰

Additional details regarding calculation of UC-100 scores will be provided in the SAP.

- **Patient-reported Outcomes (PROs)**: The following instruments will be used for the assessment of additional PROs, health-related quality of life, and healthcare utilization. All instruments are to be completed by subjects:
 - **IBDQ**⁵⁴: The IBDQ is a well-established assessment to measure disease-specific health-related quality of life. It is composed of 32 items and 4 domains including gastrointestinal symptoms, systemic symptoms, emotional dysfunction, and social dysfunction. Questionnaire items have a 2-week recall period and are scored on a 7-point Likert scale from worst health (1) to best health (7) ([APPENDIX 11](#)).

[figure not shown]
- **UC-related Hospitalization and Surgeries:** This instrument provides questions/prompts representative of the data to be collected through eCRF regarding subjects' UC-related hospitalizations and surgical procedures ([APPENDIX 12](#)).

Table 10: Selected Endpoint Definitions

Endpoint	Definition
Clinical response	Achieving the following changes in the modified Mayo score: 
 • A decrease from baseline in the modified Mayo score of ≥ 2 points, and • A decrease from baseline in the modified Mayo score $\geq 30\%$, and • A decrease in RB subscore of ≥ 1 point or absolute RB subscore ≤ 1
Clinical remission (modified Mayo score)	A modified Mayo score ^a with the following: 
 • SF subscore ≤ 1, with ≥ 1 point decrease from baseline, and • RB subscore = 0, and • Modified ES^b subscore ≤ 1
Clinical remission (total Mayo score)	
 • A total Mayo score^a ≤ 2, with no individual subscore > 1
Symptomatic remission	A symptomatic Mayo score ^a with the following: 
 • SF subscore ≤ 1, with ≥ 1 point decrease from baseline, and • RB subscore = 0
Corticosteroid-free remission	Clinical remission in subjects using oral corticosteroids at baseline who have discontinued corticosteroids for UC in the OLE period for ≥ 12 weeks prior to Week 52
Durable clinical response	Clinical response at Week 12, which is maintained at Week 52
Endoscopic remission	Mayo ES subscore = 0
Endoscopic improvement	Mayo ES subscore $\leq 1^b$
Endoscopic response	A decrease from baseline of ≥ 1 point in Mayo ES subscore

Table 10: Selected Endpoint Definitions

Endpoint	Definition
Durable endoscopic response	Endoscopic response at Week 12 which is maintained at Week 52

ES = endoscopic; OLE = open-label extension; RB = rectal bleed; SF = stool frequency; UC = ulcerative colitis

a See [Section 9.1.2](#) and [APPENDIX 9](#) for a description of the total, modified, and symptomatic Mayo scores.

b Obtained from centrally-read endoscopy ([Section 9.1.1](#)). Friability is not included in the modified definition of ES = 1.

9.2 Adverse Events

The definitions of an AE or SAE can be found in [APPENDIX 3](#).

AEs will be reported by the subject (or, when appropriate, by a caregiver, surrogate, or the subject's legally authorized representative).

The investigator and any designees are responsible for detecting, documenting, and reporting events that meet the definition of an AE or SAE and remain responsible for following up AEs that are serious, considered related to the study treatment or the study, or that caused the subject to interrupt or discontinue study treatment before completing the study.

Contacts for SAE reporting are specified in APPENDIX 3.

9.2.1 Time Period and Frequency for Collecting AE and SAE Information

The collection of nonserious AE information should begin at initiation of study treatment and continue until the follow-up visit at Week 56 or the last visit, at the time points specified in the Schedule of Activities ([Section 2](#)). Nonserious AE information should also be collected from the start of the treatment period at Day1. The Reference Safety Information [REDACTED] should be used to determine the expectedness of SAEs for expedited reporting.

All AEs related to SARS-CoV-2 infection, and all SAEs, must be collected from the time of signing the consent to the end of the safety follow-up period (within 30 days of treatment discontinuation) or roll-over into a follow-on study.

The investigator must report any SAE that occurs after these time periods and that is believed to be related to study drug or protocol-specified procedure (eg, a follow-up skin biopsy).

- Medical occurrences that begin before the start of study treatment but after obtaining informed consent will be recorded on the appropriate section of the eCRF module.

- All SAEs and AEs related to SARS-CoV-2 infection (including a positive diagnostic SARS-CoV-2 test) will be recorded and reported immediately to the Sponsor or designee but no later than 24 hours after awareness of the event, as indicated in [APPENDIX 3](#).
- The investigator will submit any updated SAE data to the Sponsor or designee immediately but no later than 24 hours of updated information being available.

Investigators are not obligated to actively seek AEs or SAEs in former study subjects. However, if the investigator learns of any SAE, including a death, at any time after a subject has been discharged from the study, and he/she considers the event reasonably related to the study treatment or study participation, the investigator must promptly notify the Sponsor or designee.

The method of evaluating and assessing causality of AEs and SAEs and the procedures for completing and reporting/transmitting SAE reports are provided in [APPENDIX 3](#).

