5 STUDY DESIGN

5.1 Overall Design

Study IM011127 is a Phase 2 randomized, double-blind, placebo-controlled, multicenter clinical study designed to assess the safety and tolerability, efficacy, [REDACTED] and biomarker response of BMS-986165 12 mg BID in subjects with moderate to severe UC. The primary objective is to estimate the effect of BMS-986165 on clinical response at Week 12 (Table 10).

The duration of study participation is approximately 60 weeks (420 days) in 4 periods, as follows:

[figure not shown]
- Screening period: up to 4 weeks (28 days; Section 5.1.1)
- Double-blind treatment period: 12 weeks (84 days; Section 5.1.2)
- OLE period: up to 40 weeks (280 days; Section 5.1.3)
- Posttreatment follow-up period: 4 weeks (28 days; Section 5.1.4)

Assessments of medical and UC disease history; prior medications, concomitant medications, and UC medications; tobacco use; baseline SF; physical examinations; chest x-ray (CXR); 12-lead ECG; and blood, stool, and urine sample collections; endoscopies with biopsies; additional efficacy assessments, PGA, PROs; and eligibility assessment will be performed as indicated in the Schedule of Activities (Section 2). Subjects will be closely monitored for AEs throughout the study.

The primary endpoint of this study is the proportion of subjects in clinical response at Week 12. This is assessed using the modified Mayo score. This instrument utilizes data from 2 sources: (1) PROs, ie, SF and RB captured by the subject in their electronic daily diary (modified Mayo score and total Mayo score); and (2) Centrally-read endoscopic assessments (modified Mayo score and total Mayo score). In addition, the physician-reported PGA, assessed by the investigator or designee at each study visit, will also be captured to facilitate the calculation of the total and partial Mayo scores. Efficacy will also be assessed using additional instruments, such as the UC-100 instrument (which uses the modified Mayo score SF and ES subscores [REDACTED]). Consequently, accurate and timely collection of each of these types of data (or samples that contribute to these data) is critical to the assessment of efficacy in this study. Additional detail on data capture for efficacy assessment and the efficacy instruments used in this study are given in Section 9.1.1.

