7.7 Concomitant Therapy

All medications taken from within 4 weeks before the first dose of study treatment until 30 days after the last dose of IP or last visit (whichever comes later) must be recorded on the appropriate eCRF.

Other than existing treatment for UC (with restrictions as described in the eligibility criteria [[Section 6](#)]), concomitant medications (prescription, over-the-counter [OTC], or herbal) should be

administered during the study only if they are prescribed for treatment of specific medical reasons separate from UC.

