9.2.5 Pregnancy

If, following initiation of the study treatment, it is subsequently discovered that a participant is pregnant or may have been pregnant at the time of study exposure, including during and at least for 30 days after study product administration, the investigator must immediately notify the BMS Medical Monitor/designee of this event and complete and forward a Pregnancy Surveillance Form to BMS Designee within 24 hours of awareness of the event and in accordance with SAE reporting procedures described in [APPENDIX 3](#).

Follow-up information regarding the course of the pregnancy, including perinatal and neonatal outcome and, where applicable, offspring information must be reported on the Pregnancy Surveillance Form. Protocol-required procedures for study discontinuation and follow-up must be performed on the participant.

Any pregnancy that occurs in a female partner of a male study subject should be reported to Sponsor or designee. In order for the Sponsor or designee to collect any pregnancy surveillance information from the female partner, the female partner must sign an ICF for disclosure of this information. Information on this pregnancy will be collected on the Pregnancy Surveillance Form.

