10.4.2.1 Adverse Events

Treatment-emergent AEs (TEAEs) are defined as AEs that occur after the subject received first dose of study treatment or if a preexisting condition worsens in severity or becomes serious after receiving the first dose of study treatment up to 30 days after the last dose of study treatment. All reported TEAEs, SAEs, deaths, AEs leading to study treatment discontinuation, and target AEs will be summarized by the Medical Dictionary for Regulatory Activities (MedDRA) SOC and PT.

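### Nonserious AEs are counted as treatment-emergent to 30 days after the last dose, but their collection ends at a follow-up visit nominally at 28 days with a ±7-day window

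*Combined protocol and SAP*

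**What the plan says.** **Counting rule.** Section 10.4.2.1 defines treatment-emergent AEs as those that start or worsen after the first dose, "up to 30 days after the last dose of study treatment".

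**Collection rule for nonserious AEs.** Section 9.2.1 says that collection "should begin at initiation of study treatment and continue until the follow-up visit at Week 56 or the last visit".

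**Collection rule for SAEs and SARS-CoV-2 AEs.** The same section runs these from consent "to the end of the safety follow-up period (within 30 days of treatment discontinuation) or roll-over into a follow-on study".

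**Where the visit falls.** Table 2 (Section 2) puts Week 52 at Day 365 with a window of ±3 days, and the Week 56 follow-up visit at Day 393 with a window of ±7 days. No column follows it. Section 5.1 lists a "Posttreatment follow-up period: 4 weeks (28 days" days) entry among the study periods, and Section 5.1.4 gives the same four weeks to OLE decliners, to Week 52 completers who do not roll over, and to those who stop study drug permanently.

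**Follow-up after discontinuation.** Section 8.1.2 says: "Subjects who discontinue study treatment will continue to be followed for 28 days post last dose of study drug". The sentence goes on to allow longer follow-up where needed, with reference to Section 9.2.3. The same section waives the Week 56 visit for subjects who roll over.

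**Other 30-day rules.** Concomitant medication is recorded "until 30 days after the last dose of IP or last visit (whichever comes later") under Section 7.7. Pregnancy notification covers exposure "including during and at least for 30 days after study product administration" under Section 9.2.5.

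**The concern.** The analysis counts events over a fixed 30 days after the last dose. For nonserious AEs, the data behind that count stop at a visit that nominally comes at 28 days and may be held earlier. A subject who follows the schedule exactly is therefore unobserved for the end of the counting window. A subject seen early loses more of it, and a subject seen on day 30 or later loses none. The length of post-treatment observation then depends on visit timing and not on the definition.

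The safety endpoint in Table 3 is the number and proportion of subjects with AEs throughout the study, and Section 5.1.6 describes this as the first exposure of UC patients to doses above 6 mg BID. An unplanned shortfall in post-treatment AE collection is worth removing when it costs little to do so.

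Nothing else in the protocol closes the gap. Section 9.2.3 follows events that have already been identified and does not schedule a search for new ones. Section 9.2.1 relieves investigators of any duty to look for AEs in subjects who have left the study.

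**Working it through.** **Inputs**
- Counting window: 30 days after the last dose (Section 10.4.2.1).
- Week 52 visit: Day 365, ±3 days (Table 2).
- Follow-up visit, where nonserious AE collection ends: Day 393, ±7 days (Table 2, Section 9.2.1).
- Assumption: the last dose is taken on the day of the Week 52 visit.

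**The plan's own figures reproduce.** 393 - 365 = 28 days, the stated follow-up. 28 + 84 + 280 + 28 = 420 days = 60 weeks, the stated duration.

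**Formula.** Days from last dose to follow-up: D = (393 + follow-up shift) - (365 + Week 52 shift). Uncollected days = max(0, 30 - D).

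**Week 52 completers who do not roll over**

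| Week 52 shift | Follow-up shift | D | Uncollected of 30 days |
|---|---|---|---|
| 0 | 0 | 393 - 365 = 28 | 2 (7%) |
| 0 | -7 | 386 - 365 = 21 | 9 (30%) |
| 0 | +7 | 400 - 365 = 35 | 0 |
| +3 | 0 | 393 - 368 = 25 | 5 (17%) |
| +3 | -7 | 386 - 368 = 18 | 12 (40%) |
| -3 | 0 | 393 - 362 = 31 | 0 |

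The rows with a Week 52 shift hold the follow-up visit to nominal Day 393. If follow-up is instead counted from the actual last dose, as 28 ±7 days, the largest shortfall is 30 - 21 = 9 days.

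**Sensitivity to the last-dose day.** Counting 84 + 280 = 364 treatment days puts the last dose on Day 364. The 2, 9 and 12 days then become 1, 8 and 11.

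**Subjects who discontinue treatment.** Section 8.1.2 counts from the last dose and gives 28 days or longer. Read as a minimum, it leaves at most 30 - 28 = 2 days. Table 2 nevertheless permits the visit 7 days early, at 28 - 7 = 21 days. The two cannot both govern, and the text does not say which does.

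**OLE decliners.** They have four weeks of follow-up (Section 5.1.4) and no Day 365 visit, so the Day 365/393 arithmetic does not describe them. On a nominal 28 days the gap is again 2 days.

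**Roll-over subjects.** They have no Week 56 visit and may go on to receive treatment in the extension study. They are a separate case and are not covered by these figures.

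**The case against.** The strongest reply is that this is a two-day wording mismatch. Safety analyses are descriptive (Section 10.4.2), and the visit rules are the same in every arm. Subjects who enter the OLE keep attending visits past Week 12, so events within 30 days of their last double-blind dose remain under collection. Any trial with visit windows has some variation in observation time. All of this stands, and it is why the expected effect is modest. It does not remove the mismatch, which is present on schedule and larger when the early window is used.

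Three stronger readings are tempting, and the documents do not support them.

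- **That the ±7-day window by itself costs 12 days.** It costs 9. Twelve also needs Week 52 at +3 days and follow-up anchored to nominal Day 393, and it can apply only to Week 52 completers.
- **That post-treatment AEs in general go uncollected.** SAEs and SARS-CoV-2 AEs already have a 30-day rule, and related SAEs must be reported even later. What remains open for these is only that no contact is scheduled at day 30. The gap concerns nonserious AEs unrelated to SARS-CoV-2, and it vanishes when the visit is on day 30 or later.
- **That the concomitant medication and pregnancy rules also conflict with the visit.** Section 7.7 takes the later of 30 days and the last visit, so it allows the two to differ. Section 9.2.5 is a duty to notify when a pregnancy comes to light and sets no visit. They show that 30 days is the usual limit in this protocol, and no more.

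A late visit that records events beyond day 30 is also no error. Leaving those out of the count is what a 30-day limit is meant to do.

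**Conclusion.** The mismatch is real and should be corrected. The collection period for nonserious AEs unrelated to SARS-CoV-2 is shorter than the window in which they are counted, by 2 days on schedule. For Week 52 completers who do not roll over it can reach 9 days within the follow-up window, and 12 days in the one combination described. For subjects who discontinue treatment it is about 2 days if Section 8.1.2 governs, but Section 8.1.2 and the -7-day window in Table 2 contradict each other and must be reconciled.

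These figures rest on the last dose being taken on the Week 52 visit day. The 12-day figure also rests on windows tied to nominal study days. The documents give no basis for estimating how many subjects would be seen early or how many events would be missed, and they show no bias between 12 mg BID and placebo. The likely effect on AE counts is modest. The case for acting is that the protocol contradicts itself and the correction is cheap.

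**What to change.** Reconcile Table 2 and Sections 5.1.4, 8.1.2, 9.2.1 and 10.4.2.1 around one end-point:

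- Place the existing follow-up visit at 30 days after the last dose, with no early window (-0/+7 days).
- State in Section 9.2.1 that nonserious AEs are collected through Day 30 after the last dose, as SAEs are.
- Carry the change into the synopsis (study periods and total duration), Section 5.1, Section 5.3 and the Week 56 row of Table 13. Amending only the safety sections would create new inconsistencies.

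No visit is added. The cost is about 2 more days of follow-up per subject (28 + 84 + 280 + 30 = 422 days in place of 420) and a narrower visit window for sites.

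Aligning the wording of Sections 9.2.1 and 10.4.2.1 without moving the visit would also remove the contradiction between those two sections. It would either shorten the counting window or leave its last days without a scheduled contact, and the early window in Table 2 would still conflict with Section 8.1.2.
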